## **Pharmacogenetics Analyses**

Specific genes may be studied that encode the drug targets, or drug mechanism of action pathways, drug metabolizing enzymes, drug transporters, or which may underpin adverse events, disease risk or drug response. These candidate genes may include a common set of ADME (Absorption, Distribution, Metabolism and Excretion) genes that are studied to determine the relationship between gene variants or treatment response and/or tolerance.

In addition, continuing research may identify other enzymes, transporters, proteins or receptors that may be involved in response to treatment. The genes that may code for these proteins may also be studied.

Genome-wide scans involving a large number of polymorphic markers (e.g., single nucleotide polymorphisms) at defined locations in the genome, often correlated with a candidate gene, may be studied to determine the relationship between genetic variants and treatment response or tolerance. This approach is often employed when a definitive candidate gene(s) does not exist and/or the potential genetic effects are not well understood.

If applicable and PGx research is conducted, appropriate statistical analysis methods will be used to evaluate pharmacogenetic data in the context of the other clinical data. Results of PGx investigations will be reported either as part of the main clinical study report or as a separate report. Endpoints of interest from all comparisons will be descriptively and/or graphically summarized as appropriate to the data. A detailed description of the analysis to be performed will be documented in the study reporting and analysis plan (RAP) analysis plan or in a separate pharmacogenetics RAP, as appropriate.

## **Informed Consent**

Subjects who do not wish to participate in the PGx research may still participate in the clinical study. PGx informed consent must be obtained prior to any blood/saliva being taken for PGx research.

## **Provision of Study Results and Confidentiality of Subject's PGx Data**

GSK may summarize the PGx research results in the clinical study report, or separately, or may publish the results in scientific journals.

GSK does not inform the investigator, subject, or anyone else (e.g., family members, study investigators, primary care physicians, insurers, or employers) of individual genotyping results that are not known to be relevant to the subject's medical care at the time of the study, unless required by law. This is due to the fact that the information generated from PGx studies is generally preliminary in nature, and therefore the significance and scientific validity of the results are undetermined.

**Appendix 2: Cockcroft-Gault Formula**

|                             |                                                                                                                                          |
|-----------------------------|------------------------------------------------------------------------------------------------------------------------------------------|
| CL Cr (mL/min) = | $Q \times (140 - \text{age}[\text{yr}]) \times \text{ideal body wt} [\text{kg}]^*$
$72 \times \text{serum creatinine} [\text{mg/dL}]$ |
| Q = 0.85 for females        |                                                                                                                                          |
| Q = 1.0 for males           |                                                                                                                                          |
| OR                   |                                                                                                                                          |
| CL Cr (mL/min) = | $K \times (140 - \text{age}[\text{yr}]) \times \text{ideal body wt} [\text{kg}]^*$
$\text{Serum creatinine} [\text{umol/L}]$          |
| K = 1.0 for females         |                                                                                                                                          |
| K = 1.23 for males          |                                                                                                                                          |

\*Calculation of Ideal Body Weight Using the Devine Formula [[Devine](#), 1974]

Ideal body weight

Males = 50.0 kg + (2.3 kg x each inch over 5 feet) or 50.0 kg + (0.906 kg x each cm over 152.4 cm)

Females = 45.5 kg + (2.3 kg x each inch over 5 feet) or 45.5 kg + (0.906 kg x each cm over 152.4 cm)

Example 1: Male, actual body weight = 90.0 kg, height = 68 inches.

Ideal body weight = 50.0 + (2.3) (68-60) = 68.4 kg.

*This subject's actual body weight is > 30% over ideal body weight. Therefore, in this case, the subject's ideal body weight of 68.4 kg should be used in calculating estimated creatinine clearance.*

[figure not shown]

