**Table 2 Definitions for Adequate Baseline Organ Function**

| System                                                 | Laboratory Values            |
|--------------------------------------------------------|------------------------------|
| Hematologic                                     |                              |
| ANC                                                    | $\geq 1.2 \times 10^9/L$     |
| Hemoglobin                                             | $\geq 9 \text{ g/dL}$        |
| Platelet count                                         | $\geq 100 \times 10^9/L$     |
| PT/INR a and PTT                            | $\leq 1.3 \times \text{ULN}$ |
| Hepatic                                         |                              |
| Total bilirubin                                        | $\leq 1.5 \times \text{ULN}$ |
| AST and ALT                                            | $\leq 2.5 \times \text{ULN}$ |
| Renal                                           |                              |
| Serum creatinine b                          | $\leq 1.5 \text{ mg/dL}$     |
| Cardiac                                         |                              |
| Left Ventricular Ejection fraction (LVEF) c | $\geq \text{LLN by ECHO}$    |

1. Abbreviations: ALT = alanine transaminase; ANC = absolute neutrophil count; AST = aspartate aminotransferase; INR = international normalized ratio; LLN = lower limit of normal; PT = prothrombin time; PTT = partial thromboplastin time; ULN = upper limit of normal.

- a. Subjects receiving anticoagulation treatment may be allowed to participate with INR established within the therapeutic range prior to randomization.
- b. If serum creatinine is  $> 1.5 \text{ mg/dL}$ , calculate creatinine clearance using standard Cockcroft-Gault formula ([Appendix 2](#)). Creatinine clearance must be  $\geq 50 \text{ mL/min}$  to be eligible.

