| Serum creatinine increase >0.2 mg/dL (18 umol/L) but ≤ 0.5 mg/dL (44 umol/L) above baseline                 | 
 
Recheck serum creatinine within 1 week
 
Serum creatinine increase > 1 week: contact GSK Medical Monitor
 
If pyrexia is present, treat pyrexia as per guidelinesa
 
                                                                                                                                                                                                                                                                                                                                                      | 
 
Continue study treatment at the same dose level
 
                                                                         |
| Serum creatinine increase >0.5 mg/dL (44 umol/L) above baseline or serum creatinine >2 mg/dL (> 177 umol/L) | 
 
Monitor serum creatinine ≥ 2-times per week
 
Hospitalization may be necessary if serum creatinine cannot be monitored frequently
 
If pyrexia is present, treat pyrexia per guidelinesa
 
Consult nephrologist if clinically indicated
 
Perform renal biopsy if clinically indicated, for example: 
 
Renal insufficiency persists despite volume repletion
 
Subject has new rash or signs of hypersensitivity (such as elevated eosinophil count)
 
 
 
 | 
 
Interrupt study treatment until serum creatinine recovers to baseline
 
Restart with study treatmentb
 
 |

1. Abbreviations: GSK = GlaxoSmithKline; NSAIDs = non-steroidal anti-inflammatory drugs

a. NSAIDs can induce renal insufficiency, especially in subjects with dehydration; encourage oral fluids or consider intravenous fluids as clinically indicated. See guidelines for pyrexia [5.7.5.1](#).

b. Investigator may restart at either the same or a reduced dose level. Escalation of study treatment to previous dose level is allowed if another episode of renal insufficiency does not occur after 4 weeks of dose reduction. Consultation with GSK Medical Monitor is required before restarting study treatment if there is evidence of thrombotic microangiopathy.

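### Appendix 2 offers two Cockcroft-Gault forms that disagree by about 4% for women, so a borderline woman can meet the 50 mL/min eligibility criterion by one form and fail it by the other

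*Protocol*

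**What the plan says.** Protocol Appendix 2 sets out creatinine clearance in mL/min in two forms joined by the word OR. Both have the same numerator apart from the sex constant: 140 minus age, times ideal body weight.

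- mg/dL form: the denominator is 72 times serum creatinine, with "Q = 0.85 for females" and "Q = 1.0 for males".
- umol/L form: the denominator is serum creatinine alone, with "K = 1.0 for females" and "K = 1.23 for males".

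The appendix gives no rule for choosing between them.

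The equation is used for eligibility. Table 2 (Section 4.1.2) accepts serum creatinine up to 1.5 mg/dL. Above that, its footnote b tells the site to "calculate creatinine clearance using standard Cockcroft-Gault formula", refers to Appendix 2, and requires at least 50 mL/min. Table 21, footnote 2, repeats the mg/dL trigger. Section 4.1.2 allows no deviation from the inclusion criteria, and Section 7.3.3 says that subjects whose laboratory values fall outside the eligibility limits should be excluded.

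**The concern.** Two forms of one equation that differ only in the creatinine unit must give the same clearance for the same subject. For men they do. For women the printed constants do not correspond, and nothing elsewhere in the protocol reconciles them. Because the result is compared with a fixed limit that allows no deviation, a woman close to the limit has two protocol-compliant answers, one eligible and one not. What is at stake is the consistency of one screening decision. No objective, sample size or analysis depends on it.

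**Working it through.** **Inputs**
- From Appendix 2: Q = 0.85 (women) and 1.0 (men), denominator constant 72; K = 1.0 (women) and 1.23 (men).
- Limit of 50 mL/min, applied when creatinine exceeds 1.5 mg/dL: Table 2, footnote b.
- Conversion factor f, in umol/L per mg/dL. Table 14 pairs the two units three times. One pair is "serum creatinine >2 mg/dL (> 177 umol/L", giving 177/2 = 88.5. The others are 0.5 mg/dL with 44 umol/L (f = 88) and 0.2 mg/dL with 18 umol/L (f = 90, coarsely rounded). The usual factor of 88.4 is not in the documents. It is used here as an assumption and lies within the range of these pairs.

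**Check without a conversion factor**

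The ratio of women's to men's constants must be the same in both forms.
- mg/dL form: 0.85/1.0 = 0.850
- umol/L form: 1.0/1.23 = 0.813

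Rounding of the male constant does not explain this. If 1.23 stands for anything from 1.225 to 1.235, the female constant should be 0.85 × 1.225 = 1.041 to 0.85 × 1.235 = 1.050.

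**Check with a conversion factor**

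Equating the two forms gives K = Q × f/72.

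Men, as a reproduction of the printed figure: 88.4/72 = 1.228 and 88.5/72 = 1.229. Both round to 1.23.

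Women:

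| f | implied K = 0.85 × f/72 | printed 1.0 relative to implied K | mg/dL result at which the umol/L form gives exactly 50 |
|---|---|---|---|
| 88 | 1.039 | 3.7% lower | 51.9 |
| 88.4 (assumed) | 1.044 | 4.2% lower | 52.2 |
| 88.5 | 1.045 | 4.3% lower | 52.2 |
| 90 | 1.0625 | 5.9% lower | 53.1 |

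The last column is 50 × implied K. No factor in the range gives 1.0.

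**Example at the limit**

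Woman aged 30, height 66 inches, creatinine 1.51 mg/dL.
- Ideal body weight by the appendix: 45.5 + 2.3 × 6 = 59.3 kg.
- mg/dL form: 0.85 × 110 × 59.3/(72 × 1.51) = 51.0 mL/min, which meets the criterion.
- umol/L form, with creatinine 1.51 × 88.4 = 133.5 umol/L: 1.0 × 110 × 59.3/133.5 = 48.9 mL/min, which does not.

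**How many women could be in this position**

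The equation matters only above 1.5 mg/dL. To reach 50 mL/min there by the mg/dL form, a woman needs (140 − age) × weight above 50 × 72 × 1.5/0.85 = 6353. With ideal body weight, that means an age of about 23 or younger at 64 inches (54.7 kg), 32 or younger at 66 inches (59.3 kg), and 47 or younger at 70 inches (68.5 kg). She must then also fall in a band about 2 mL/min wide.

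**The case against.** The strongest reply is that the discrepancy will hardly ever operate. Table 19, note 14, assigns chemistry to the central laboratory, so creatinine would normally come from one source. The criterion and the trigger are both in mg/dL, so whoever applies footnote b as written already holds an mg/dL value and would naturally use the mg/dL form. The eligible group is very small, as the last step of the check shows. The study ended with 6 patients enrolled (SAP Section 3.1), and SAP Section 4 says laboratory data will be neither summarized nor listed, so no reported result depends on the constant.

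All of this stands as a limit on the size of the point. It does not remove the conflict. Section 7 lets routine clinical tests done before consent serve for screening if they meet the protocol's conditions, Table 14 itself works in both units, and Appendix 2 leaves the form open even for a central laboratory value.

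A reader might infer that the eligibility limit itself shifts with the laboratory's units, or that sites did reach different answers. The documents support neither. The limit stays at 50 mL/min and only a woman's calculated clearance changes. Different answers between sites are possible, but nothing shows that any occurred.

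**Conclusion.** The point holds as a small internal inconsistency in an operative rule. For women, the umol/L form in Appendix 2 gives a clearance about 4% below the mg/dL form (3.7% to 4.3% for factors of 88 to 88.5). The existence of the conflict needs no outside figure, since it follows from the printed constants alone; only its exact size depends on the factor. The printed value looks like 1.04 rounded to one decimal while the male constant kept two, although the documents do not say so.

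The consequence is confined to women with creatinine above 1.5 mg/dL and a clearance of about 50.0 to 52.2 mL/min by the mg/dL form. It runs one way: the umol/L form can exclude such a woman but cannot admit one who fails by the mg/dL form. The age and height figures assume ideal body weight, as the formula states. The appendix's worked example may suggest actual weight for some subjects, which would change those figures but not the 4%, because weight cancels between the forms. It would be wrong to infer that anyone was wrongly excluded or that any result is affected.

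**What to change.** Reconcile the two forms so that one subject has one answer. Either of two changes does this:

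- Print the female umol/L constant to the same precision as the male one, that is 1.04, as the protocol's own mg/dL form implies. The forms then agree within about 0.5% for factors of 88 to 88.5. At 88.4 the remaining band is 50.0 to 50 × 1.0436/1.04 = 50.2 mL/min.
- Name one governing form for eligibility. This leaves no residual difference.

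The cost is one constant or one sentence in an appendix, with no effect on design, data collection or analysis. With enrolment ended, the practical value lies in correcting the text before it is reused in another protocol.

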**Appendix 3: Liver Chemistry Monitoring, Interruption Stopping and Follow-up Criteria**

**Phase II Liver Safety Algorithms**

#### **Appendix 4: Country Specific Requirements**

No country-specific requirements exist.

## Appendix 5: Collection of CSF

Cerebrospinal fluid may be collected as an optional procedure on the same day as the resection of the melanoma brain metastasis(es). Signed, informed consent must be obtained prior to the surgical procedure. At the time of surgery, up to 3 mL of CSF can be collected only if the neurosurgeon attests that there are not any signs of intracranial hypertension (e.g. bulging of brain tissue through the craniotomy site due to recent intratumoral hemorrhage). Any of the four ways described below can be followed to collect CSF

1. In select cases after the dura is opened, the neurosurgeon will determine if there is a sulcus that is large enough to permit puncture with a 25 gauge butterfly needle attached to a 1 mL tuberculin syringe such that CSF can be slowly withdrawn (see figure on the following page).
2. If the operative exposure permits the surgeon will access one the basal cisterns, in a similar manner as above, CSF will be withdrawn after puncture with a 25 gauge butterfly.
3. Depending on the craniotomy exposure, an image-guided trajectory to the lateral ventricles may be possible. In these cases, if there is no access using the above methods, the pia/arachnoid will be coagulated with bipolar cautery and image guidance will determine a trajectory to allow ventricular puncture with a ventricular catheter and CSF will be withdrawn. The trajectory may be through the cortical surface or after the resection, through the tumor cavity into the ventricle.

If the above methods are not possible, a lumbar puncture will be performed while still under general anesthesia following the completion of the craniotomy and resection of the CNS tumor. The patient will thus be placed in lateral position on the operating table and standard sterile technique for lumbar puncture will be done to withdraw up to 3 mL of CSF.

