of the brain and whole-body PET-CT imaging will also be performed between 1 to 3 days prior to surgery. On the day of surgery, blood samples will be collected for pharmacokinetic analysis. Two samples will be collected prior to surgery, and two samples will be collected after surgery; all samples will be separated in time by at least 1 hour. Optional collection of CSF will be obtained in the operating room on the day of brain metastasis resection; this procedure is described in Section 6.5 of the protocol. Portions of the resected brain metastasis(es) that in the clinical judgment of the neurosurgeon performing the operation are not required to be submitted for pathological confirmation of melanoma brain metastasis will be divided into sections to be used for pharmacokinetic, pharmacodynamic, and exploratory translational research studies. Optional collection of an easily accessible extracranial metastasis may be performed after the PET-CT scan and up to 1 day after the removal of brain metastasis(es); which will be similarly divided for studies. The time of collection of brain metastasis, the plasma samples, and the optional extracranial metastasis(es) and CSF will be recorded for the purpose of the pharmacokinetic analysis, as well as the time the last dose of study treatment was taken.

Subjects in either cohort with intracranial and/or extracranial metastases remaining after surgery may resume treatment with the combination of dabrafenib 150 mg BID and trametinib 2 mg once daily no earlier than 72 hours after surgery at the discretion of the Principal Investigator. Subjects continuing on treatment will be evaluated for safety 4 weeks after restarting treatment, and every 4 weeks thereafter. These subjects will be evaluated for efficacy eight weeks after restarting treatment, and every 8 weeks thereafter.

[figure not shown]
Subjects who do not continue treatment after the craniotomy procedure will be evaluated for safety at the discontinuation visit 4 weeks after the craniotomy.

All subjects who permanently discontinue study treatment will be followed for survival and new anti-cancer therapy for a total of two years or until death or the subject wishes to withdraw from further follow-up. The study will be considered closed once the last subject reaches this milestone.

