#### **6.5. Treatment of Study Treatment Overdose**

In the event of a dabrafenib overdose, defined as administration of more than 300mg as a single dose or 600mg daily (the highest dose tested in clinical studies to date), and/or a trametinib overdose, defined as administration of more than 3.0 mg once daily (the maximum tolerated dose defined in the MEK111054 study), the investigator should contact the GSK Medical Monitor immediately and closely monitor the subject for AEs/SAEs and laboratory abnormalities. GSK does not recommend specific treatment. The investigator will use clinical judgment to treat any overdose.

Decisions regarding dose interruptions or modifications should be made by the investigator in consultation with the Medical Monitor based on the clinical evaluation of the subject.

A plasma sample for PK analysis may be requested by the Medical Monitor on a case-by-case basis. This plasma sample should be collected as soon as possible.

Information regarding the quantity of the excess dose as well as the duration of the overdosing should be documented in the eCRF.

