#### **7.4.3. CSF Collection for Pharmacokinetics**

Collection of CSF will be an optional procedure; subjects must provide consent for this procedure. CSF will be collected either right before cutting the dura, on condition that there is no evidence of intracranial hypertension, or using the lumbar puncture approach (following completion of craniotomy and repositioning the subject while under general anesthesia during the same operation OR postoperatively), or accessing the Ommaya reservoir, if present. Three ml of CSF will be processed for pharmacokinetic analysis and quantified using an investigative LC-MS/MS method. The time of CSF collection will be recorded for the comparative pharmacokinetic analyses.

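### Section 7.4.3 permits an optional research lumbar puncture, in the same operation or postoperatively, without the intracranial-hypertension condition that Appendix 5 sets for CSF taken at surgery

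*Protocol*

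**What the plan says.** CSF is an optional sample that needs the subject's consent, and it supports a secondary pharmacokinetic endpoint (Protocol Table 1, Sections 7.4.1 and 7.4.3). Three places in the protocol describe how it is obtained.

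Appendix 5 is the detailed procedure. For sampling at the time of surgery it states that "CSF can be collected only if the neurosurgeon attests that there are not any signs of intracranial hypertension". Its example of such a sign is brain tissue bulging through the craniotomy after recent bleeding into the tumour. It then lists four ways of collection:

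- Sulcal puncture: "In select cases after the dura is opened, the neurosurgeon will determine if there is a sulcus" large enough to enter.
- Puncture of a basal cistern.
- A ventricular catheter: "The trajectory may be through the cortical surface or after the resection, through the tumor cavity into the ventricle".
- If none of these is feasible, "a lumbar puncture will be performed while still under general anesthesia following the completion of the craniotomy".

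Section 7.4.3 gives three routes. The first is sampling "either right before cutting the dura, on condition that there is no evidence of intracranial hypertension". The second is lumbar puncture and the third an existing reservoir; the sentence ends "during the same operation OR postoperatively), or accessing the Ommaya reservoir, if present". No pressure condition follows the second or third route.

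Section 3 says that CSF will be "obtained in the operating room on the day of brain metastasis resection; this procedure is described in Section 6.5 of the protocol". Section 6.5 is about something else. It begins: "In the event of a dabrafenib overdose, defined as administration of more than 300mg as a single dose".

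**The concern.** The protocol treats raised intracranial pressure as a reason not to take CSF at surgery, yet one of its two procedural texts carries that condition for a single route only. Lumbar puncture is the route where the omission matters, because Section 7.4.3 lets it be done under the same anaesthetic or later, with no stated check.

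The sample is for research and is optional, so the safeguard around it should not depend on which section a site happens to read. Read alone, Section 7.4.3 would let a site puncture after a craniotomy without anyone recording that signs of raised pressure had been looked for. What is at stake is subject safety in an optional procedure. The primary brain and plasma concentrations do not depend on it.

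**Working it through.** No sample size, power or event figure enters this point, so there is nothing to compute. The check is to set the texts side by side.

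| Route | Section 7.4.3 | Appendix 5 |
|---|---|---|
| Intracranial, before the dura is cut | Allowed, with the condition | Not listed |
| Sulcal, cisternal or ventricular, at open operation | Not listed | Allowed, with the attestation |
| Lumbar puncture, same operation | Allowed, no condition attached | Allowed as fallback, with the attestation |
| Lumbar puncture, postoperative | Allowed, no condition attached | Not listed |
| Ommaya reservoir | Allowed, no condition attached | Not listed |

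**Scope of each condition.** In Section 7.4.3 the three routes are alternatives in one sentence and the condition sits inside the first. It covers 1 of 3 routes, or 1 of 4 options if the two lumbar puncture timings are counted separately. In Appendix 5 the attestation comes before the list and governs all 4 ways, the lumbar puncture included.

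**Same-operation lumbar puncture.** Appendix 5 conditions it and Section 7.4.3 does not. Section 7.4.3 omits the condition without waiving it, so a site that follows Appendix 5 meets both texts.

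**Whether the site would find Appendix 5.** Section 7.4.3 does not cite it. In the supplied protocol it is named only in the table of contents and at its own heading. The one pointer to the CSF procedure, in Section 3, leads to the overdose section. The Study Procedures Manual is not the place to settle the matter, because Section 3 confines it to content that does not bear on safety.

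**Postoperative lumbar puncture.** Appendix 5's attestation is worded for the time of surgery and its lumbar puncture is under the same anaesthetic, so it does not reach a later puncture. Section 7.4.3 sets no condition. Neither text therefore requires a check.

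**Fit with the rest of the protocol.** Section 3 places collection in the operating room and, further on, at the craniotomy. Section 7.4.1 places it at the resection. Appendix 5 places its lumbar puncture within the same anaesthetic. The Protocol Summary and Table 19 fix only the day of surgery, so they neither support nor exclude a later puncture that day. The postoperative option stands alone in Section 7.4.3.

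**Dural timing.** Section 7.4.3 samples just before the dura is cut. Appendix 5's first way is after it is opened, and its third may follow the resection. The two texts share no intracranial route.

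**The case against.** The strongest reply is that Appendix 5 is part of the protocol and is the dedicated procedure. A site bound by the whole document must obtain the attestation for any CSF taken at surgery, whatever Section 7.4.3 leaves unsaid. On that view all that remains is one stray postoperative alternative, at odds with the other descriptions and best read as a drafting slip.

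There are other safeguards too. Section 4.1.3 excludes subjects whose neurological symptoms are not controlled on steady or falling steroids. Section 3 requires a brain MRI 1 to 3 days before surgery and a physical examination the day before. Section 7.8 calls for imaging within 72 hours after the craniotomy. In both texts lumbar puncture comes only after the craniotomy is complete.

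Most of this stands. For the same-operation puncture it reduces the point to a missing condition and a missing cross-reference. It does not close the postoperative gap. The symptom criterion is applied before study treatment, which starts 7 to 14 days before surgery. The pre-operative MRI precedes the operation. The 72-hour imaging is not tied to a puncture and could come after it. None of these is a check at the time of puncture.

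Three stronger readings are tempting, and the documents do not support them:

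- A reader might infer that the two texts cannot both be obeyed. For a same-operation puncture they can.
- A reader might infer that the protocol set up a postoperative puncture programme without safeguards. One alternative in one sentence, contradicted elsewhere, does not show that.
- A reader might take the 6% of subjects with an intracranial haemorrhage serious adverse event, reported in Section 1.2 for the earlier phase II brain-metastasis trial, and project a number at risk here. That figure covers a whole treatment course in a different trial, and nothing links it to raised pressure at a lumbar puncture after resection. It does not measure this defect.

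**Conclusion.** The inconsistency is real and worth correcting. A same-operation lumbar puncture is conditioned in Appendix 5 and unconditioned in Section 7.4.3, and a reader of Section 7.4.3 is not led to the stricter text. A postoperative lumbar puncture is conditioned in neither, and the option does not fit the places that tie collection to the operation.

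Its size is modest. It concerns an optional, consented procedure for a secondary endpoint. The documents report no harm from CSF collection, and the primary endpoint is unaffected. SAP Section 3.1 records that the study was terminated with 6 subjects enrolled, so the change would protect no further subject in this trial. Its value is a consistent record and safer wording if the text is reused.

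The conclusion rests on the supplied text alone. It assumes that no document outside the protocol and SAP already imposes a check before a lumbar puncture. How many subjects, if any, had one is not stated.

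**What to change.** 1. In Section 7.4.3, delete the postoperative alternative for lumbar puncture. If it is kept, require a separate documented clinical or imaging check for raised intracranial pressure before the puncture. Extending Appendix 5's attestation is not enough there, because its only example, brain bulging through the craniotomy, cannot be seen after closure.
2. Apply the no-intracranial-hypertension attestation to every CSF route in Section 7.4.3, including same-operation lumbar puncture and Ommaya access.
3. Keep the Ommaya route and add it to Appendix 5. Simply making Appendix 5 the only procedure would drop that route without saying so.
4. Cross-refer Section 7.4.3 to Appendix 5, and state in both whether intracranial sampling is before or after the dura is opened.
5. Change the Section 3 pointer from Section 6.5 to Section 7.4.3 and Appendix 5.

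The cost is wording in three places of the protocol. The downside is that a few optional CSF samples may not be taken. No change to the analysis or to the SAP listings is needed for this point.
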